2. SUMMARY OF PROPOSALS

2.1 ABSTRACT:

The detection of malarial retinopathy (MR) in cerebral malaria (CM) patients currently requires expensive equipment and extensive training. We have developed a computerized software-based analysis of retinal images obtained by handheld fundus cameras that is >90% specific. The purpose of this study is to evaluate the performance of a software in detecting malarial retinopathy in retinal images obtained using hand-held fundus cameras by non-ophthalmologist clinicians. The overall aim of the proposed study is to collect digital retinal image data of clinically diagnosed CM patients and utilize the images to develop and test the performance of software algorithms (ASPIRE) for detecting specific signs of MR and for detecting the presence of MR. The performance of the software will be measured against the binocular indirect ophthalmoscopy (BIO) examination (if available) performed by an ophthalmologist for determining the presence of MR (reference standard) and/or against the grading of established retinal graders. Participants between the age of 6 months and 12 years who present with coma, a positive malaria test, and clinical diagnosis of CM, will be enrolled at the time of admission at the respective participating hospital(s). The imager will be masked to MR detection results. The retinal images will be graded by an ophthalmologist for the detection of specific signs of MR. The retinal images will be used to develop and test algorithms for detecting specific MR lesions and overall MR presence. The sensitivity and specificity of the software algorithms against grader's image grading will be determined to evaluate the performance of each algorithm and its usability in identifying MR. This study would be a first step in the validation of retinal image analysis software for assessment of MR. The results of the

study will be used to inform initiatives to spread the use of software-based detection of MR to preclinical settings in which CM patients are seen. Results will also be useful in planning the studies to quantify the detection of MR lesions and analyze large datasets in objective manner.

LAY SUMMARY OF RESEARCH PROTOCOL

The detection of malarial retinopathy (MR) in cerebral malaria (CM) patients currently requires expensive equipment and extensive training. We have developed a computerized software-based analysis of retinal images obtained by handheld fundus cameras that is >90% specific. The purpose of this study is to evaluate the performance of a computer software in detecting malarial retinopathy in retinal images obtained using up to three different hand-held fundus cameras in the hands of non-ophthalmologist clinicians.

The overall aim of the proposed study is to collect digital retinal color image data from 800 clinically diagnosed CM patients from the malaria endemic regions of Nigeria and Malawi and utilize the images to develop and test the performance of software algorithms (ASPIRE) for detecting specific signs of MR and for detecting the presence of MR. The performance of the software will be measured against the binocular indirect ophthalmoscopy (BIO) examination (if available) performed by an ophthalmologist for determining the presence of MR (reference standard) and/or against the grading of established retinal graders. From March 2021 or as soon as the ethics committee

approves the protocol, children aged between 6 months and 12 years who present with coma, a positive malaria test, and clinically confirmed diagnosis of cerebral malaria will be enrolled at the time of admission at the respective participating hospitals. After obtaining informed consent from the parent/guardian, both eyes will be dilated, and photos of the eyes will be collected using each of the three different cameras. There are no risks that are involved in taking part in this study. All the other procedures such as collection of samples are standard procedures in the diagnosis of malaria. Findings from this study will help in the development of a low cost system that will be integrated to a smartphone that will help clinicians in low-income countries to clearly diagnose MR.

3. INTRODUCTION.

3.1. BACKGROUND:

Cerebral malaria (CM) is a life-threatening clinical syndrome associated with malarial infection. As per the *World Malaria Report 2019*, sub-Saharan Africa experienced 213 million cases of malaria (93% of the global cases) in 2018 and an estimated 381,000 deaths that included 256,000 deaths of children under the age of five (1). Most of these mortalities were thought to be caused by CM. Because individuals in malaria-endemic areas can be infected with the malaria parasite without being symptomatic, the clinical syndrome of CM may or may not be caused by the malaria parasites detected in the blood. An incorrect diagnosis leads to incorrect treatment (2,3). Therefore, non-malarial comas which have high fatality rates may go undiagnosed and result in potentially avoidable death (4). Lewallen et al. (5) and Taylor et al. (i) found that nearly a quarter of children who died with a clinical diagnosis of CM actually had other non-malarial causes of death.

An accurate diagnostic to confirm the presence of CM is critically needed to improve clinical outcomes. Lewallen et al. (3) described a constellation of retinal lesions

associated with CM, called malarial retinopathy (MR). The characteristic features include retinal whitening, vessel discoloration, and white-centered hemorrhages (ii). Since MR was found to be greater than 90% sensitive and specific for the presence of the histologic hallmark of CM, the sequestration of parasitized red cells in the cerebral microvasculature (iii), retinal screening for MR represents an effective means for improving the specificity of CM diagnosis. In the past 2 decades, it has been demonstrated that around 60% of children in the CM research project in Blantyre, Malawi manifest MR of some degree. Children without detectable MR are significantly more likely to have another diagnosis or to be the children who respond most quickly to anti-malarial treatment. Thus, examining comatose children for the retinopathy is a useful prognostic sign, and in areas of high malaria endemicity it can help guide clinicians. It may also be useful in following the changes in the epidemiology of cerebral malaria in areas where public health interventions have been implemented.

Although BIO has been the reference standard for identifying MR, it is important to recognize that it is not a true “gold standard.” Fundus photography with a modified digital camera, and even examination with direct ophthalmoscopy (DO), which both provide higher magnification than BIO, sometimes demonstrate the “abnormal vessels” of MR when they were not recognized by BIO. DO is cheaper and easier to learn than BIO but it does not provide a good alternative to BIO since it allows examination only of a narrow field of view within the posterior pole. Studies comparing the sensitivity of BIO to digital photography for detecting MR have not been carried out; in the future, such studies could

be useful to researchers seeking further understanding of the pathophysiology of CM and MR.

Now that simple, low cost fundus imaging systems such as the Pictor-Plus retinal camera (Volk Optical), VistaView, and iNview cameras are available, the possibility exists for providing digital images to clinicians in low resource settings where CM is common. This could impact the diagnosis and treatment of CM. The ability to visualize the fundus would also allow for the possibility of assessing the presence of papilledema, a valuable prognostic feature in comatose patients, irrespective of the cause of the coma. Digital retinal color image data of clinically diagnosed CM patients will be collected and utilized to develop and test the performance of software algorithms for detecting specific signs of MR and for detecting the presence of MR. The performance of the software will be measured against the binocular indirect ophthalmoscopy (BIO) examination (when available) performed by an ophthalmologist for determining the presence of MR (reference standard) or image grading from a certified retinal grader.

Handheld and easy-to-use retinal imaging systems can provide good quality color fundus images. A recent (unpublished) pilot study conducted in Malawi indicated that ophthalmic experts using handheld and smartphone based retinal cameras had sensitivity in the range of 87%-100% and specificity in the range of 75%-87% for the detection of the presence of any signs of MR, against those detected by an experienced ophthalmologist using BIO. The results of this study were encouraging and justify our efforts in moving forward to the next steps for automated analysis of retinal images for detection of MR.

Automated analysis of retinal images and a computer-assisted retinal disease diagnosis have proven to be useful in detecting number of eye diseases including diabetic retinopathy and age-related macular degeneration. An automated software for detection of MR lesions and diagnosis of MR and its integration with a portable and low-cost retinal camera will be convenient for use in non-ophthalmic, non-clinical settings, making it highly accessible and affordable to the targeted population where other CM diagnostic methods are limited.

3.2 PROBLEM STATEMENT:

Considering the malaria-endemic regions in Africa that lack adequate number of ophthalmologists, a fully automated software system for the comprehensive analysis of MR abnormalities and detecting the presence/absence of MR would be useful. This would also mitigate the challenges of training the healthcare staff to use ophthalmoscopes and/or to read and grade the retinal images. The software system can be tuned to yield high specificity, addressing the current clinical requirement to prevent deaths resulting from misdiagnosis of CM. It can also include the automated detection of papilledema, a sign of severe brain swelling and important to recognize in patients with and without CM.

3.3 JUSTIFICATION FOR THE STUDY

To date, binocular indirect ophthalmoscopy (BIO) with a 20-diopter lens by an experienced examiner (usually an ophthalmologist) is the “reference test” method for diagnosing MR. With BIO, the examiner is able to obtain a wide angle, relatively low

magnification view of the retina. BIO has been used as the diagnostic standard in all studies that demonstrate associations of MR with outcomes and other factors. BIO is inherently limited as a diagnostic tool as it depends greatly on the examiner's experience and skill. Even among experienced ophthalmologists, there may be disagreements on findings; most non-ophthalmologists do not practice enough ophthalmoscopy to be proficient in the skill. Attempts to teach non-ophthalmologist clinicians (NOC) to use BIO in CM clinical settings in Africa have generally been disappointing (with a few exceptions) due to the time required to learn the technique and the lack of personnel (particularly ophthalmologists) to provide ongoing supervision. Thus, in most settings where CM is treated in Africa, the fundus signs are not sought or missed.

Given a clear retinal image, clinicians learn relatively easily to recognize specific patterns that are common to specific diseases (e.g., diabetic retinopathy screening). Modern digital imaging techniques capture excellent images of the fundus and are used widely now for screening for eye conditions. Recently, new technologies, using handheld retinal cameras and smartphone-based retinal cameras, allow fundus imaging to be done simply and inexpensively. These open the possibility, for the first time, of providing many clinicians who treat children in malaria-endemic areas with high quality fundus photos of children with clinically defined CM. The analysis of the images is not straightforward, and unfortunately, there is a scarcity of ophthalmic experts capable of analyzing retinal images and determining the presence or absence of MR routinely in clinical settings in Africa.

3.4 GENERAL OBJECTIVE

The overall aim of the proposed study is to collect digital retinal color image data of clinically diagnosed CM patients and utilize the images to develop and test the performance of software algorithms for detecting specific signs of MR and for detecting the presence of MR. The performance of the software will be measured against the binocular indirect ophthalmoscopy (BIO) examination (if available) performed by an ophthalmologist or image grading from a certified retinal grader.

3.5 SPECIFIC OBJECTIVES

The primary objectives are:

1. To collect mydriatic retinal images of at least N= 50 pediatric subjects clinically diagnosed with CM at each of the study sites located in Nigeria, Africa. Retinal images will be collected from the participating clinics/hospitals by clinicians over a period of 2 years. The activity has been piloted and found to be within the scope of clinicians in Nigeria.
2. To determine the sensitivity and specificity of software algorithms for classifying clinically diagnosed CM patient into MR positive or MR negative using the images obtained with up to three retinal cameras, compared with retinal graders' grading (in all cases) and the clinical reference standard (BIO) when possible.

Secondary objectives are:

1. To determine the positive predictive value (PPV) and negative predictive value (NPV) of software algorithms for classifying clinically diagnosed CM patient into MR positive

or MR negative using the images obtained with up to three retinal cameras, compared with retinal graders' grading (in all cases) and the clinical reference standard (BIO) when possible.

2. LITERATURE REVIEW:

Cerebral malaria (CM) is a fatal neurological syndrome of malarial disease. The *World Malaria Report 2019* estimates that malaria claimed 381,000 lives in Africa in 2018, over 65% of whom were children under five years of age [iv]. CM is one of the largest contributors to pediatric malarial deaths, and approximately 23% of children are found to be misdiagnosed with CM, which leads to incorrect treatment and results in mortality or neurological disability in thousands of children in Africa [v,vi,vii,viii,ix]. There is a significant market need for low-cost and easy-to-use technology to improve CM diagnosis and save lives.

Malarial Retinopathy (MR) manifests as a series of retinal lesions highly specific (>95%) to CM and therefore can be used to improve the diagnostic accuracy of CM. VisionQuest proposes the development and clinical deployment of an artificial intelligence (AI) system, Auto Detection Software for Plasmodium Infection in Retinal Exams (ASPIRE), that offers the first AI-supported MR detection software integrated with a low-cost and portable retinal camera, a system that can be operated by minimally trained personnel such as medical technician or nurse without the need of an ophthalmic specialist.

Societal and Economic Significance. As per the *World Malaria Report 2019*, sub-Saharan Africa experienced 213 million cases of malaria (93% of the global cases) in 2018 [iv] and an estimated 381,000 deaths that included 256,000 deaths of children under the age of five. These children are particularly susceptible to severe malarial infection and its fatal syndrome, CM, which affects over 2 million children annually [6] and remains one of the major killer of children in Africa. However, up to 23% of these children's deaths are thought to be caused by nonmalarial diseases, such as pneumonia, that mimic CM

symptoms and lead to misdiagnosis of CM [v,vi,vii,viii,ix]. The high rate of CM misdiagnosis and incorrect treatment of these concurrent diseases often results in death or has long-lasting socioeconomic impacts on survivors in the form of neurologic disabilities [x]. Malaria results in a loss of USD \$12 billion in GDP per year in Africa and 35.4 million disability-adjusted life years due to mortality and morbidity, to which CM is one of the major contributors [iv]. These deaths and co-morbidities could be prevented by a highly specific test for CM, such as ASPIRE, which will alleviate this economic burden by increasing the accuracy of CM diagnosis, leading to accurate treatment of underlying diseases, and saving lives [x].

Clinical Significance. CM is caused by the *Plasmodium falciparum* (*Pf*) parasite, which causes retinal abnormalities unique to MR such as retinal whitening and white-centered hemorrhages. For a comatose patient who tests positive for *Pf*, MR screening improves the specificity of CM diagnosis from 61% (World Health Organization [WHO] criteria for CM diagnosis) to 100% (WHO criteria + MR screening) [v]. However, African countries lack adequate numbers of ophthalmologists and enough ophthalmic equipment to screen for MR and to serve the affected population; for example, Malawi has only four ophthalmologists treating a population of 18 million. *ASPIRE provides an AI-supported and highly specific test that increases the positive predictive value (PPV) of CM diagnosis and can be used by a minimally trained non-ophthalmic health-care provider.* ASPIRE is designed to fulfill the clinical need in Africa with a low-cost, portable, and quick diagnostic tool, which makes it ideal for bedside diagnosis.

Clinical Benefit. The true prevalence of CM in clinically diagnosed cases is 77% (23% false positives) [v]. The use of ASPIRE (specificity = 95%) in addition to the WHO criteria

(specificity = 61%) increases the PPV of CM diagnosis from 0.89 to 0.99 and reduces the number of misdiagnosed CM patients from 11% to 1%. Based on a yearly incidence of clinically diagnosed CM patients between 2 and 2.5 million, the use of ASPIRE in addition to WHO criteria can reduce the number of misdiagnosed patients by over 200,000, leading to appropriate diagnosis, correct treatment, and saved lives.

The proposed project will lead to the rollout of the first AI-supported bedside tool for detection of malarial retinopathy to improve accuracy in diagnosis of cerebral malaria. ASPIRE was *designed in response to* three major clinical needs in Africa: First, it can be operated by minimally trained (or non-ophthalmic) personnel, thus addressing the shortage of ophthalmologists in African countries. ASPIRE will thus be in demand by a variety of healthcare services from major hospitals to individual community healthcare workers that can use ASPIRE effectively. Second, ASPIRE is designed to be affordable (~USD \$1,500), portable, and easily accessible to the affected population. Third, ASPIRE can be augmented with software modules to detect other equally preventable retinal diseases, such as diabetic retinopathy (DR) and hypertensive retinopathy (HTR), thus increasing its cost-effectiveness.

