3. METHODOLOGY

STUDY SITE

This study will be conducted within the malaria endemic regions of Nigeria. The study population will be enrolled at each of the following study sites located within the malaria endemic region of Nigeria;

1. University College Hospital, Ibadan
2. Amino Kano University, Kano
3. General Sani Abacha Specialist Hospital, Damaturu
4. State Specialist Hospital, Sokoto
5. Massey's Children Hospital, Lagos Island

STUDY DESIGN^[1-5]

This will be a prospective, pivotal, multi-center clinical study.

STUDY POPULATIONS

Study participants involved in this study will be children aged between 6 months and 12-year-old who have been diagnosed with cerebral malaria.

Inclusion Criteria:

- Children aged 6 months- 12 years admitted to any one of the study sites who satisfy the standard clinical case definition of cerebral malaria

- Blantyre coma score of ≤ 2
- Known results of a positive malaria test (blood smear or malaria rapid diagnostic test)
- Consent provided by parents/caregivers of the eligible children.

Exclusion criteria:

- Children admitted who satisfy the standard clinical case definition of cerebral malaria, but when there is no clinician/nurse available to do an examination within 6 hours of admission.

SAMPLING^[1-3]

Sample size determination

We aim to demonstrate MR detection performance on a validation dataset collected with continuous enrollment of clinically diagnosed CM patients with or without malarial retinopathy. About 61% of CM-diagnosed patients show a manifestation of CM in retina, in form of retinal lesions, called malarial retinopathy (MR) [xi,xii,xiii]. Rest 39% of CM-diagnosed patients do not exhibit MR. So, the prevalence of MR in CM-diagnosed patients is 61%.

The study hypothesis is that the sensitivity and specificity of detecting MR using ASPIRE's MR detection algorithm is non-inferior to the clinical reference standard, which is defined as the reading of retinal images for MR detection by ophthalmic specialists such as ophthalmologists.

Non-Inferiority test design:

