According to literature studies, the sensitivity and specificity of ophthalmologists in reading retinal images to detect retinal diseases are 89% and 87%, respectively [xiv]. We aim to demonstrate that the sensitivity and specificity of our software-based test are non-inferior to the ophthalmologist's standard, with 7% non-inferiority margin [xv]. Therefore, the lower-bound on both sensitivity and specificity will be at least equal or greater than the minimum sensitivity and specificity requirements for a diagnostic software as recommended by the FDA, of 80% and 80%, respectively.

The study will use a non-inferiority design and seek to demonstrate that the experimental method (software-based reading of retinal images) is not appreciably worse than the standard method (ophthalmologist's reading of retinal images). The reason behind using a non-inferiority design is that the proposed software-based test is not expected to be better than the standard test (ophthalmologist's reading of retinal images) on a primary efficacy end point in clinical study; but the availability, accessibility, affordability, and compliance of the proposed software-based test will be better outside the clinical study and hence efficacy will be better outside the study. Therefore, the proposed software-based test has potential to provide greater clinical benefit and/or outcome at the cost of being non-inferior in performance compared to the standard test [xvi].

In this study design, we used Blackwelder formula [xvii,xviii] to calculate sample size:

$$N_{cases} = \frac{(Z_\alpha + Z_\beta)^2}{(\pi_S - \pi_E - d)^2} \left[\pi_E(1 - \pi_E) + \frac{\pi_S(1 - \pi_S)}{\lambda} \right],$$

where

$$\lambda = \left(\frac{1 - Prev}{Prev} \right).$$

The conjectured accuracy (sensitivity/specificity) of the standard test is π_s , the conjectured accuracy (sensitivity/specificity) of the proposed diagnostic/experimental test is π_E . $Z\alpha$ and $Z\beta$ are standard values assuming 80% power and 5% Type-I error. "Prev" is prevalence of disease-positive patients, and "d" is a non-inferiority margin.

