To establish that our software-based test is non-inferior to the standard test (ophthalmologist’s reading of images), with sensitivity of 0.89 and specificity of 0.87; we will require a minimum number of disease-positive (MR-positive) “cases” of 366, and minimum number of disease-negative (MR-negative) “controls” of 234. In total, we will require a minimum sample size of 600 CM-diagnosed patients to validate our proposed test.

Once we enroll the minimum number of MR-positive and MR-negative patients required, we propose to validate the software-based test performance on the collected sample and verify if the resulting sensitivity/specificity is within the margin of difference. Upon verification, it can be concluded that the experimental test is non-inferior to the standard test within a non-inferiority margin of 7%.

Sampling procedure [11]

The procedure will be as follows:

1. Pupillary light response is checked and then pupils are dilated with 0.5% tropicamide and 10% phenylephrine, repeated after 10 minutes.
2. Ophthalmologist, clinician or nurse takes iNview photos (at least 8 photos: 4 optic disc center, 4 macula center)
3. Ophthalmologist, clinician or nurse takes VistaView photos (at least 8 photos: 4 optic disc center, 4 macula center)
4. Ophthalmologist, clinician or nurse takes Pictor-Plus photos (at least 8 photos: 4 optic disc center, 4 macula center)
5. The retinal photos captured by Pictor-Plus, VistaView, and iNview cameras may be transmitted to a laptop computer or smartphone automatically and analyzed instantaneously for image quality by a computer-based software. The software will either accept or reject each photo based on high or low image quality, respectively. A graphical display on a laptop computer or smartphone

will be shown to the imager (ophthalmologist, clinician, or nurse) that demonstrates the captured image and whether it was accepted or rejected.

6. The retinal photos captured by Pictor-Plus, VistaView, and iNview cameras will be analyzed instantaneously for detection of malarial retinopathy (MR) by a computer-based software. The imager (ophthalmologist, clinician, or nurse) will be masked to MR detection results due to non-interventional nature of this study.
7. The analysis of retinal photos for image quality and MR detection will be fully automatic and handled by a laptop computer or smartphone and will not require manual inputs or interference from the imager.
8. Ophthalmologist performs BIO when possible.

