The following conditions apply to the steps above:

- a) All the children will have the retinal images taken and when possible, a BIO (if available) conducted by an ophthalmologist as part of the study component.
- b) Fundus examination and photography will be done as soon as the pupils are a minimum of 6 mm or not more than 1-hour post dilation.
- c) The order of steps 2-4 can be interchanged or some of the steps can be omitted (depending upon camera availability) at the discretion of the ophthalmologist/clinician/nurse but once determined, efforts will be followed consistently with each patient.
- d) Ideally the examinations will take place within a few minutes of each other, but if this is not possible, no more than 2 hours between examinations will be accepted

(due to possibility of changes in the clinical features). The camera images are time stamped so that this can be verified.

- e) The data collection form will be the “standard form” used in previous studies of MR.

The retinal image data obtained using Pictor-Plus, VistaView, and iNview will be analyzed by an independent retinal grader masked to the ophthalmologist’s findings in the BIO exam.

EXAMINATION PROCEDURE FOR RETINAL CAMERAS (Pictor-Plus, VistaView, iNview)

The right eye will be examined first with slow “panning” in image mode of the disc, the macula, the horizontal raphe, along all four main vascular arcades, and a 360-degree survey outside the arcades. The left will be examined the same way. These procedures may have to be modified if the eyes are deviated or the head position is restricted due to intravenous catheter. Images collected by Pictor-Plus, VistaView, and iNview will be transmitted to a laptop computer or smartphone automatically and analyzed instantaneously for image quality by a computer-based software. The software will either accept or reject each photo based on high or low image quality, respectively. A graphical display on a laptop computer or smartphone will be shown to the imager (ophthalmologist, clinician, or nurse) that demonstrates the captured image and whether it was accepted or rejected. Further, the images will be analyzed instantaneously for detection of malarial retinopathy (MR) by a computer-based software. The imager (ophthalmologist, clinician, or nurse) will be masked to MR detection results. The images will be independently graded by a retinal grader masked to the BIO exam and clinical status. The user will

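### The plan does not say which camera, or what pooled result, carries the single non-inferiority claim behind the 600-patient calculation

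*Combined protocol and SAP*

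**What the plan says.** - **Objective.** Section 3.5, primary objective 2, classifies each child as MR-positive or MR-negative "using the images obtained with up to three retinal cameras".
- **Hypothesis.** Section 3, Sample size determination, states one hypothesis, for sensitivity and specificity: that ASPIRE's "MR detection algorithm is non-inferior to the clinical reference standard". It names no camera.
- **Error and power.** The normal deviates in the sample size formula "are standard values assuming 80% power and 5% Type-I error". Neither figure is divided among cameras.
- **Sample size.** The conclusion of that section reads: "In total, we will require a minimum sample size of 600 CM-diagnosed patients to validate our proposed test". The split is 366 MR-positive and 234 MR-negative, with no minimum per camera.
- **Procedure.** Sampling procedure steps 2 to 4 take a separate set of at least 8 photos with each of iNview, VistaView and Pictor-Plus. Step 6 runs the MR software on the photos from all three.
- **Omission.** Condition (c) under those steps says that "some of the steps can be omitted (depending upon camera availability) at the discretion of the ophthalmologist/clinician/nurse", and then adds "but once determined, efforts will be followed consistently with each patient".
- **Conflicting statement.** The lay summary in section 2 says "photos of the eyes will be collected using each of the three different cameras".

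**The concern.** The calculation is for one test that gives one result per child. The procedure can give up to three results per child, and a different number from one site to another. The legible text does not designate a primary camera, combine cameras into one patient-level result, set a minimum per camera, or control error across cameras.

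Two things are at stake. If the deciding camera is settled after the results are known, the chance of a false non-inferiority claim exceeds 5%. If the deciding camera was skipped in part of the sample, its power falls below 80%. The study describes itself as pivotal and proposes to conclude non-inferiority. The device appendix shows that the cameras are not identical (40-degree field for Pictor-Plus, 50-degree for iNview), so a reader needs to know which imaging the claim covers.

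**Working it through.** **Inputs from the plan (section 3, Sample size determination).** Sensitivity 0.89 and specificity 0.87, each assumed equal for software and standard; margin d = 0.07; prevalence 0.61, so λ = 0.39/0.61 = 0.639; 5% error; 80% power. The plan does not state whether the 5% is one-sided. The formula is taken as printed.

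**Step 1: reproduce the plan's figure.** With equal rates p, cases = (Zα + Zβ)² / d² × p(1 − p)(1 + 1/λ), and controls = λ × cases.

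- One-sided 5%: (1.645 + 0.842)² / 0.07² ≈ 1,261.8, and 1 + 1/λ = 2.564.
- Specificity: 1,261.8 × 0.1131 × 2.564 = 365.9, so 366 cases and 234 controls, total 600. This matches.
- Sensitivity: 1,261.8 × 0.0979 × 2.564 = 316.7, so 317 cases and 203 controls. The plan has 318 and 203, which agrees apart from rounding.
- Two-sided 5% gives 762 for specificity and does not reproduce, so one-sided 5% is used below.

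**Step 2: a camera named in advance and used in all 600.** Power = Φ(d/SE − 1.645), with SE = √[p(1 − p)(1/cases + 1/controls)].

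- Specificity: SE = √[0.1131 × (1/366 + 1/234)] = 0.02815; 0.07/0.02815 − 1.645 = 0.842; power 80.0%.
- Sensitivity: SE = 0.02619; 0.07/0.02619 − 1.645 = 1.028; power 84.8%.

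Its error remains 5%, because it is the only test that decides.

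**Step 3: any one of the cameras may carry the claim.** Take one measure exactly at the margin, tested at one-sided 5% on each camera. The upper bound is 3 × 5% = 15%. With independent tests the error is 1 − 0.95³ = 14.3%. The same children are imaged, so the results should be correlated. Simulation of equicorrelated normal test statistics (1,000,000 draws; correlations are assumptions) gives:

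| Correlation | Two cameras | Three cameras |
|---|---|---|
| 0 | 9.8% | 14.3% |
| 0.5 | 8.8% | 11.8% |
| 0.7 | 8.0% | 10.3% |
| 0.8 | 7.5% | 9.2% |
| 0.9 | 6.8% | 8.0% |

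These figures apply when the other measure is almost certain to pass. If both measures must pass, both sit at the margin and they are independent, the error per camera is 0.05 × 0.05 = 0.25%. Over three independent cameras it is 1 − 0.9975³ ≈ 0.75%.

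**Step 4: a camera omitted in part of the sample.** The same power formula, with the 61/39 split retained. The shares are assumptions, since the plan gives none.

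| Children with the camera | Specificity | Sensitivity |
|---|---|---|
| 600 | 80% | 85% |
| 540 | 76% | 81% |
| 480 | 72% | 77% |
| 400 | 65% | 70% |
| 360 (220/140) | 61% | 66% |
| 300 (183/117) | 55% | 60% |

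For 360: specificity SE = √[0.1131 × (1/220 + 1/140)] = 0.03636; 0.07/0.03636 − 1.645 = 0.280; power 61%.

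**Step 5: paying for three claims by Bonferroni.** At one-sided 5%/3 = 1.67% each, 600 children on every camera leave 64% power for specificity and 71% for sensitivity. Restoring 80% for specificity takes 522 + 334 = 856 children on each camera.

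**The case against.** The strongest reply is that the plan intends one patient-level result. Objective 2 classifies the patient, and the sample size section speaks of a single software-based test. On that reading there is one test and no multiplicity across cameras. The reading is possible, but no legible passage says how images from different cameras are combined, or what happens when one is absent. A pool of whichever cameras were used would be a different test at different sites.

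Several further points stand:

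- Under study question #2 in Data Analysis, the list of comparisons is absent from the available text. It may have named camera comparisons, so its absence is not held against the plan. A list would settle the matter only if it also said which comparison decides.
- The 14% is a worst case. It needs independent cameras and one measure at the margin while the other is nearly sure to pass.
- Condition (c) asks for consistency once the choice is made, and the lay summary expects all three cameras. Consistency limits ad hoc switching, but a site that consistently skips a camera still reduces that camera's numbers.
- The availability shares are illustrative. The lay summary gives 800 patients across Nigeria and Malawi; three-fifths of that is 480, with 72% and 77% power rather than 61% and 66%.

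A reader might go further and infer that the stated 5% and 80% hold for no camera at all, or that the plan permits choosing the best camera after seeing results. The documents support neither. Step 2 shows that a camera fixed in advance and used throughout keeps both figures, and no passage authorises a choice after the results. The plan is silent on the choice.

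**Conclusion.** The concern holds in this form: the plan does not identify the camera or pooled result to which its single 5%/80% calculation applies. The 600 is correct for one predefined result available in all 600 children.

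If any of three cameras may count, the one-sided error for a measure at the margin is about 8% to 14% over assumed correlations of 0.9 to 0, and lower if both measures must pass and both are at the margin. If the deciding camera is missing in part of the sample, power falls, for example to 61% (specificity) and 66% (sensitivity) at 360 of 600, or 55% and 60% at 300 of 600. The power figures use the plan's own formula and rates at one-sided 5%; the shares are assumed.

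This is more than a missing detail. Following the procedure as written can produce several camera results, or a mix that varies by site, for one pivotal claim. It should be fixed before analysis, because a choice made once results are known cannot be credibly repaired.

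**What to change.** 1. Before any analysis, designate one primary result in primary objective 2 and in the sample size conclusion. It can be either one named camera, with a stated rule for turning its photos of both eyes into one result per child, or a predefined pooled patient-level rule that also covers children in whom a camera was not used.
2. Count the 366 MR-positive and 234 MR-negative minimum on children who have that result.
3. Make the other camera results secondary, with estimates and confidence intervals and no non-inferiority claim. If more than one camera must carry a claim, test them in a fixed order stated in advance.
4. Reconcile the lay summary, which has all three cameras used, with condition (c) of the sampling procedure, which lets steps be omitted. If a single camera is primary, its step should not be one that may be omitted.

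The text change is small, and the total stays at 600 if the primary result is obtained in every child. The real costs are that the sponsor must commit in advance and that a single primary camera must be available at every site. Where supply makes that doubtful, the pooled rule serves as well. Whichever rule is chosen, its effect on specificity needs thought: calling a child positive on any flagged photo would tend to lower it.
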